  - An increase in corrected QT interval by Fridericia's formula (QTcF) value of >60 msec from baseline (average of baseline triplicate values) or an absolute QTcF >500 msec, both confirmed by repeat measurement after 20 minutes in resting position, and considered IMP related.

Or

- If one or more subjects in the preceding dose group experience:
  - o An increase in troponin I concentration which is considered clinically significant by the Investigator (with reference to the change from baseline value) and considered IMP related.

Or

• If the dose in a single subject is anticipated to exceed an AUC from time of dosing to the end of the dosing interval (AUC0-tau) of  $\geq$ 100 µg\*h/mL. These limits are based on the exposure observed at the 20 mg/kg in cynomolgus monkeys (no observed adverse effect level (NOAEL): AUC0-24 of 101 µg\*h/mL in male and 111 µg\*h/mL in females).

DNDi RD 777/34920 DNDi- 0690- 02

Final V3.0/ Date 07 December 2020

Confidential

Page 9 of 109

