#### Day 10:

On Day 10, only a morning dose will be administered.

- Start Holter monitoring (for extraction of ECGs) at approximately 60 minutes prior to dosing (Holter will be on for at least 25 hours and can only be removed after 24 h post-last dose PK blood samples are collected)
- Eligibility check: Pre-dose
- O Dosing (morning only on Day 10, even if BID regimen implemented)
- Laboratory safety tests (biochemistry, haematology, coagulation, urinalysis, urine microscopy): Pre-dose
- o Troponin I: Pre-dose
- o 12-lead ECG: Pre-dose and 4 h post-dose
- Vital signs (supine systolic and diastolic blood pressure, pulse rate and tympanic temperature):
   Pre-dose
- o AE
- o SAE
- Prior and concomitant medication
- PK plasma sample for DNDI-0690 and metabolite: Pre-dose and 0.5, 1, 2, 3, 3.5, 4, 6, 9, 12 h post-dose
- O DBS samples for DNDI-0690: Pre-dose and 0.5, 1, 2, 3, 3.5, 4, 6, 9, 12 h post-dose
- o PK urine samples for DNDI-0690:[0-24] h post-dose
- Urine samples for exploratory biomarkers: Pre-dose
- Full blood sampling for transcriptional profiling (mRNA) assessment (**Only performed on Cohort 2 and Cohort 3**)

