#### IMP ADMINISTRATION

**DNDi** 

RD 777/34920

DNDi- 0690- 02

Capsules of DNDI-0690 100mg and 200 mg have been chosen as the formulation for this study. The number of capsules to be administered will vary depending on the dose selected by the SRC upon review of data (safety and PK) from the previous cohort.

Table 1 Description of DNDI-0690 doses

Part A	Dose		Incurace from the provious dass
rart A	mg	mg/kg/day*	Increase from the previous dose
Cohort 1	400 OD	5.7	
Cohort 2	To be decided	To be decided	2 to 3 times and/or change from OD to BID
Cohort 3	To be decided	To be decided	2 to 3 times and/or change from OD to BID
Cohort 4	To be decided	To be decided	2 to 3 times and/or change from OD to BID
Part B	maximum of 3600	maximum of 51.5	
Part C	To be decided	To be decided	Highest dose tested in Part A and well tolerated, or below

\* assuming a 70-kg person

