## 8.5 Toxicology

### 8.5.1 Regulatory Toxicology Studies

The non-clinical safety of DNDI-0690 was assessed in repeated dose toxicity studies in rats and monkeys following oral administration of the compound daily for up to 4 weeks.

In rats, a first GLP 14-day toxicity study was conducted with DNDI-0690 formulated in polyethylene glycol (PEG) 400 and administered as single daily doses up to 250 mg/kg/day. In

DNDi RD 777/34920 DNDi- 0690- 02

Final V3.0/ Date 07 December 2020

Confidential

Page 39 of 109

this study, the NOAEL was set at 100 mg/kg/day (AUC24 on Day 14 of 93.6 and 149  $\mu g \cdot h/mL$  in males and females, respectively) since some histopathological changes in the liver (hepatocellular hypertrophy) and adrenals (cortical vacuolation and hypertrophy) were detected at the dose of 250 mg/kg/day.

Subsequent toxicity studies both in rats and in monkeys were performed using DNDI-0690 formulated as nanosuspension.

In the GLP 4-week repeated dose toxicity study in rats, only minimal reduction of body weight and food consumption, with concomitant slight decrease in globulin and total cholesterol, were seen at doses of 200 and 1000 mg/kg/day (100 and 500 mg/kg BID 6-h apart). No other effects were evidenced. Based on these findings, the dose of 40 mg/kg/day was the NOEL and the dose of 1000 mg/kg/day was the NOAEL.

In the GLP 4-week toxicity study in monkeys, doses of 20, 100 and 400 mg/kg/day (10, 50, 200mg/kg BID 6-h apart) were selected. One female died at the dose of 100 mg/kg/day and another at 400 mg/kg/day on Days 23 and 29, respectively. Deaths were related to severe effects on the heart and the kidneys, the animals were severely dehydrated, and the adverse effects on the heart being likely a consequence of renal toxicity. In other monkeys treated at these dose levels, noteworthy effects of DNDI-0690 included renal effects in females and histological changes in the testes in males (see below). Changes in the kidneys were characterized by tubular dilatation, cell degeneration and/or basophilia, associated with increases in creatinine and urea. Kidney changes completely recovered, as evidenced at the end of a 7-week recovery period. In this study, no effects were observed at the dose of 20 mg/kg/day that was considered as the NOAEL in monkeys after 4-week administration.

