A Pathology Working Group (PWG) was constituted to review the data on testes. For the 7–day study, the PWG concluded that the testicular effect of vacuolation was a background change and that the effects seen were all considered as fixation artefact and thus the testicular histology was all concluded to be within the normal. In the case of the 28-day study, the PWG confirmed following review the presence of changes in the testes of animals at the two highest doses of 100 and 400 mg/kg/day (the same animals as in the initial report) where the finding was described by the PWG as segmental tubular dilation with associated thinning/atrophy of the seminiferous epithelium. This distribution could suggest a potential relationship to treatment. However, based upon the segmental nature of the finding, the frequent unilateral distribution and the fact that this finding has been described in a number of publications as a background change in young cynomolgus monkeys, it was concluded that the findings in the testes were a background lesion and unrelated to treatment. In conclusion, treatment with DNDI-0690 for 7 or 28 days is not considered to induce any testicular changes or toxicity.

Confidential

Final V3.0/ Date 07 December 2020

Page 40 of 109

Table 3 Summary of Toxicokinetic and Pharmacokinetic Parameters for DNDI-0690\*

Species / Day	Gender	Type of study	Dose PO (mg/kg/day)	C max (µg/mL)	AUC 0-24 (μg.h/mL)
Rat /	M	Toxicology TK	1000 (500 bid) NOAEL 28 days	$11.3 \pm 0.693$	180 ± 22.5
Day 28	F	Toxicology TK	1000 (500 bid) NOAEL 28 days	16.9 ± 1.47	307 ± 36.8
Monkey /	M Toxicology TK		20 (10 bid) NOAEL 28 days	$8.03 \pm 0.367$	101 ± 7.85
Day 28	F	Toxicology TK	20 (10 bid) NOAEL 28 days	$9.03 \pm 6.78$	111 ± 61.2

\* methodology, additional doses and time-points available in the IB

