### 8.7 Risk/Benefit Assessment

No benefit will be observed in healthy volunteers.

The risk/benefit ratio of the proposed study is considered acceptable. Several measures to minimize the risks to healthy subjects have been taken with respect to the following study design elements:

- For each cohort in Part A and Part B, 2 subjects (1 subject on active drug and a subject on matching placebo) will be dosed and monitored for 48 hours prior to dosing the rest of the cohort.
- Dose escalation (during Part A and between Part A and Part B) will be done in a stepwise, controlled manner, with dose escalation only being permitted after full evaluation of the available safety data from the previous cohort by the SRC.
- Clinical laboratory monitoring: At time of study entry, study participants are required to have safety laboratory values within acceptable ranges. Serial measurements of safety laboratory parameters (Biochemistry and haematology which include platelet count, renal/liver function tests, renal integrity monitoring) and coagulation parameters are planned with interim reviews as defined in the SRC charter.
- Close cardiac safety monitoring by regular ECG assessments.
- Study eligibility: The healthy subject/patient inclusion and exclusion criteria have been incorporated to minimize any risk of an exaggerated pharmacological effect of DNDI-0690.
- The evaluation of GFR by a reference method in Part C will be performed at the end of the trial. The dose level used in Part C will be tested in Part A and will have no impact on the safety of the volunteers.
- The starting dose in Part A of this study is 400 mg once daily for 10 days which is considered to be safe and is well below the highest dose level of 3600 mg DNDI-0690 administered in the SAD study. It is expected that the maximum values of  $C_{max}$  and  $AUC_{0-24}$  in individual subjects in Part A Cohort 1 will be well below the PK stopping criteria of  $C_{max} \ge 8000$  ng/mL or  $AUC_{0-24} \ge 100,000$  ng,h/mL.

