# 10.2 Dose Escalation Procedures and Stopping Criteria

### **10.2.1 Dose Escalation Procedures (Part A and Part B)**

Following completion of each cohort in Part A, a summary of all available safety (AE, 12-lead ECG, vital signs and safety laboratory data) and 24 hour post last dose PK data (minimally Cmax and AUC0-24 data) will be produced on behalf of the PI. Planned doses may be modified following a review of emerging data. Progression to the next dose level and dose selection will be based on the available safety and PK data from all evaluable 9 subjects from the preceding dose level (a subject will be deemed as evaluable for dose escalation purposes if they have received the planned study dose and had sufficient plasma samples collected to estimate Cmax and AUC0-24 irrespective of whether they have received active or placebo treatment). Dose escalation will be dependent upon the accrual of acceptable safety and PK data. If it is not appropriate to escalate the dose according to the proposed dose escalation schedule, then the same dose, an intermediate dose or a lower dose may be given following discussion between the Sponsor and the PI (or deputy).

There will be a Telephone Conference at a pre-appointed time to involve the Simbec-Orion Project Manager and the PI (or deputy) and the Sponsor's representative(s), including the Sponsor's Responsible Physician. After discussion of all the data, the decision will be made whether to dose escalate and a written document (dose escalation approval form) signed by the PI (or deputy) and Sponsor will be produced ratifying that decision. Full minutes, to be agreed by all parties, will be produced for each discussion regarding dose escalation and filed in the investigator site file (ISF). A copy of the signed dose escalation approval form will be provided to the Simbec-Orion Pharmacist and this will allow the IMP to be assembled for the next dose level.

Part B dosing regimen will be decided after reviewing all available Part A safety and PK data following the same rules and procedures as for Part A.

Dose escalation stopping criteria are detailed in Section 10.2.2.

DNDi RD 777/34920 DNDi- 0690- 02

Final V3.0/ Date 07 December 2020

Confidential

Page 49 of 109

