#### 10.2.2.3 Dose Escalation Stopping Criteria

Dose escalation between cohorts in Part A (and between Part A and Part B) will be temporarily stopped pending evaluation of all available data if any of the following criteria are fulfilled:

• A serious adverse reaction (*i.e.* a SAE considered at least possibly related to the IMP administration) occurs in one subject.

Or

• Severe non-serious adverse reactions (*i.e.*, severe non-serious AE considered as, at least possibly related to the IMP administration) occur in two subjects in the same cohort, independent of within or not within the same system organ class.

Or

• If two or more subjects in the preceding dose group experience any of the following:

DNDi RD 777/34920 DNDi- 0690- 02

Final V3.0/ Date 07 December 2020

Confidential

Page 50 of 109

- o ALT or AST >3xULN, considered clinically significant and IMP related.
- Serum Cys C increase > 25%, confirmed after repeat assessment 24-48h apart, and considered IMP related.
- o Ratio of microalbuminuria/creatininuria >300 mg/g and considered IMP related.
- o an increase in QTcF value of >60 msec from baseline (average of baseline triplicate values) or an absolute QTcF >500 msec, both confirmed by repeat measurement after 20 minutes in resting position, and considered IMP related.

Or

- If one or more subjects in the preceding dose group experience:
  - o an increase in troponin I concentration which is considered clinically significant by the Investigator (with reference to the change from baseline value) and considered IMP related.

Or

• If the dose in a single subject is anticipated to exceed an AUC0-tau of  $\geq 100 \, \mu g^*h/mL$ . These limits are based on the exposure observed at the 20 mg/kg in cynomolgus monkeys (NOAEL: AUC0-24 of 101  $\mu g^*h/mL$  in male and 111  $\mu g^*h/mL$  in females).

Or

• If the dose in a single subject is anticipated to exceed a  $C_{max}$  of  $\geq 8.0 \ \mu g/mL$ . These limits are based on the exposure observed at the 20 mg/kg in cynomolgus monkeys (NOAEL:  $C_{max}$  of  $8.03 \ \mu g/mL$  in males and  $9.03 \ \mu g/mL$  in females).

Dose escalation between cohorts in Part A will be limited to a maximal 3-fold increase, and 2-fold increase between Part A and Part B, depending on safety and tolerability data and predicted exposure (both AUC and  $C_{max}$ ).

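### In a twice-daily (BID) Part A cohort, the 100 µg·h/mL escalation limit is set on one dosing interval although it derives from a 24 h, two-dose exposure

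*Protocol*

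**What the plan says.** The rule appears twice in the protocol. The Synopsis (Part A) stops escalation "If the dose in a single subject is anticipated to exceed an AUC from time of dosing to the end of the dosing interval" of 100 µg·h/mL or more. Section 10.2.2.3 has the same criterion: "If the dose in a single subject is anticipated to exceed an AUC 0-tau of" the same value. The abbreviation list also defines AUC0-tau as running to the end of the dosing interval.

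The stated basis is the monkey NOAEL at 20 mg/kg, with an AUC0-24 of 101 (males) and 111 (females) µg·h/mL. Section 8.5.1 shows that this was divided dosing: "doses of 20, 100 and 400 mg/kg/day (10, 50, 200mg/kg BID 6-h apart) were selected", and Table 3 labels the row "20 (10 bid) NOAEL 28 days". The reference is therefore a whole-day exposure over two doses.

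Elsewhere the limit is a 24 h AUC. Section 8.7 expects that Cmax and AUC0-24 "in individual subjects in Part A Cohort 1 will be well below the PK stopping criteria of" 8000 ng/mL and AUC0-24 100,000 ng·h/mL. Section 8.6.1 uses the same cap, also as AUC0-24, in describing the single-dose study.

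Table 1 leaves BID open for each of Cohorts 2, 3 and 4: "2 to 3 times and/or change from OD to BID". The evening dose follows 10 h after the morning dose, so the intervals are 10 h and 14 h (Section 10.5.3.1).

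The escalation review receives safety data "and 24 hour post last dose PK data", at minimum Cmax and AUC0-24 (Section 10.2.1). The Day 10 schedule reads "Dosing (morning only on Day 10, even if BID regimen implemented". The only AUC added for BID is AUC0-10, on Days 1 and 10 (Section 10.9.2.5.4). The steady-state predictions in Section 10.3.1 are for once-daily dosing.

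**The concern.** Once daily, AUC0-tau and AUC0-24 are the same quantity and the rule is sound. Under BID they differ, and the metric in the rule is the smaller one. A threshold calibrated on a full day's exposure would be compared with part of a day's exposure.

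The routine PK summaries do not correct this. Day 10 AUC0-24 includes carry-over from Day 9 but no evening dose. AUC0-10 stops where the evening dose begins. Day 1 AUC0-24 does span both doses, but it precedes steady state, and only the 12 h sample lies between the evening dose and the next pre-dose sample.

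The error is in the unsafe direction: a BID cohort could satisfy the written rule while a subject's daily AUC is above the NOAEL exposure that the limit is meant to respect. Single-dose exposure is sub-proportional, so splitting a daily dose tends to raise daily AUC while lowering the AUC0-tau that is checked.

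**Working it through.** **The plan's own figure.** Section 8.6.1 puts the single-dose maxima (3160 ng/mL; 42,600 ng·h/mL) 60.5% and 57.4% below the cap. 1 − 3160/8000 = 60.5% and 1 − 42,600/100,000 = 57.4%. Both reproduce, with the cap read as AUC0-24.

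**Inputs (Table 4, fasted males, µg·h/mL).** 1200 mg: AUC0-12 13.4, AUC0-24 19.7, AUC0-inf 25.1. 400 mg: 8.5, 11.8, 13.9. Linear superposition over time and no food effect are assumed. The highest scheduled Part A dose is 2400 mg/day (Section 10.3.1), i.e. 1200 mg BID.

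**Steady-state BID exposure at 1200 mg.**
- k = ln[(25.1 − 13.4)/(25.1 − 19.7)]/12 = 0.0644/h (half-life 10.8 h). This gives AUC0-10 = 11.8 and AUC0-14 = 14.8 after a single dose.
- Daily AUC = 2 × 25.1 = 50.2 (47.2 if Table 4's predicted AUC0-tau of 23.6 is doubled instead).
- Morning interval = AUC0-10 + (AUC24-34 + AUC14-24)/(1 − e^(−24k)) = 11.8 + (2.56 + 4.89) × 1.27 = 21.3, or 42% of daily.
- Evening interval = 50.2 − 21.3 = 28.9, or 58%.
- Day 10 AUC0-24 without the evening dose = 50.2 − 14.8 = 35.4, or 70%.
- Day 1 AUC0-24 with both doses = 19.7 + 14.8 = 34.5, or 69%.

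At 400 mg BID the daily AUC is 27.8. The corresponding values are 11.9 (43%), 15.9 (57%), 18.5 (67%) and 21.1 (76%).

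**Direction.** Log-log interpolation of Table 4 AUC0-inf between 1200 mg (25.1) and 3600 mg (47.1) gives about 37 for 2400 mg once daily, against 50.2 for 1200 mg BID.

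**What the Cmax limit leaves open.** Escalation also stops if any subject is anticipated to exceed a Cmax of 8.0 µg/mL.
- Hard bound: if concentration stays below 8.0 all day, daily AUC is below 24 × 8 = 192.
- Average profile: add carry-over to the Table 4 single-dose Cmax (1.67 µg/mL at 1200 mg, 1.12 at 400 mg), with the tail concentration C(t) = k(AUC0-inf − AUC0-12)e^(−k(t−12)) and Tmax 1.5 to 4 h (the range of medians in Section 8.6.1). At 1200 mg the steady-state morning peak is 2.84 to 2.66 and the evening peak 3.06 to 2.85. Scaling the whole profile until the peak reaches 8.0 gives a daily AUC of 50.2 × 8.0/2.84 = 142 to 50.2 × 8.0/2.66 = 151 (morning peak), or 131 to 141 (evening peak). At 400 mg the ranges are 133 to 141 and 123 to 132.

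For an average profile the Cmax rule therefore fires at a daily AUC of about 123 to 151. Day 10 AUC0-24 reaches 100 at a similar point: 100 × 50.2/35.4 = 142 (1200 mg) and 100 × 27.8/18.5 = 150 (400 mg).

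**Chance that one subject exceeds 100 at 1200 mg BID.** Lognormal, geometric mean as above, σ = √ln(1 + CV²). The CVs are the Table 4 AUC0-inf values at 3600 mg (24.2%) and 1200 mg (63.9%); 40% is an assumed intermediate.

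| CV | daily AUC | Day 10 AUC0-24 | AUC0-10 |
|---|---|---|---|
| 24.2% | 0.2% | <0.1% | <0.1% |
| 40% | 3.7% | 0.4% | <0.1% |
| 63.9% | 12% | 3.8% | 0.4% |

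**The case against.** The strongest reply is the companion Cmax rule. A reader might infer from the 42% share that a BID subject could pass with a daily AUC near 235 (100 × 50.2/21.3 = 236; 234 at 400 mg). The protocol does not allow that: an AUC0-10 of 100 means an average of 10 µg/mL over 10 h, so the 8.0 µg/mL limit would already have been exceeded. The 14 h interval reaching 100 (daily about 173) would need a mean of 7.1 µg/mL under a peak below 8.0, an almost flat profile. This stands, and it sets the size of the point.

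The trigger is also narrow. BID is allowed only if the number of capsules per intake raises acceptability concerns. At 2400 mg that is 12 capsules of 200 mg, against 18 taken at once in the single-dose study. Cohort 1 and Parts B and C are once daily. The predicted mean daily AUC at the top scheduled BID dose is half the limit.

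The rule acts on anticipated exposure, and the criterion itself cites the 24 h monkey AUC, so the SRC could superpose two doses unprompted. That is true, but the metric the rule names is AUC0-tau, and no text tells the SRC to use another under BID.

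A reader might also infer that toxicity begins just above the limit. Section 8.5.1 does not show that: renal effects and the two deaths occurred at 100 and 400 mg/kg/day, at least five times the NOAEL dose, with deaths on Days 23 and 29. Dosing here lasts at most 10 days, with renal, troponin and SAE stopping rules alongside.

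**Conclusion.** The point holds in a limited form. For a BID cohort, the written escalation limit uses a metric that does not match its source, and the Day 10 AUC0-24 supplied for the decision does not repair it. At 1200 mg BID these two quantities capture about 42% (morning interval) and 70% of daily AUC. Because of the Cmax limit, the exposure that could pass unnoticed is a daily AUC between 100 and roughly 125–150 for an average profile. Subjects with flatter profiles could sit higher, but not above 192.

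This rests on linear superposition of fasted male single-dose data, on profiles that scale proportionally, and on the Cmax limit being applied to the highest peak of the day. Exposure was higher in women and in the fed state, which would raise the probabilities. The 0.2% to 12% range comes from the choice of CV, and it is a pre-trial extrapolation that observed PK from earlier cohorts would replace. Severity is low and conditional on BID; once-daily cohorts are unaffected.

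**What to change.** In the Synopsis, Section 10.2.1 and Section 10.2.2.3, state that the 100 µg·h/mL limit applies to the anticipated steady-state AUC0-24 including all doses given in 24 h. Add that for a BID cohort this is obtained by superposition of both doses at the per-intake dose level, and that neither AUC0-tau nor the Day 10 AUC0-24 is to be compared with the limit. Section 8.7 already uses AUC0-24, so the wording would then agree throughout.

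The cost is a few sentences and a short superposition calculation, needed only if BID is chosen. Dosing times and sampling need not change. The downside is a less favourable anticipated exposure under BID, which may hold a BID cohort at a lower dose.

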#### Or

• If the dose in a single subject is anticipated to exceed a maximum concentration ( $C_{max}$ ) of  $\geq 8.0 \ \mu g/mL$ . These limits are based on the exposure observed at the 20 mg/kg in cynomolgus monkeys (NOAEL:  $C_{max}$  of  $8.03 \ \mu g/mL$  in males and  $9.03 \ \mu g/mL$  in females).

Dose escalation between cohorts in Part A will be limited to a maximal 3-fold increase, and 2-fold increase between Part A and Part B, depending on safety and tolerability data and predicted exposure (both AUC and  $C_{max}$ ).

If any of the above criteria are fulfilled, the cases will be discussed at the SRC who could proceed with partial or full unblinding as necessary to take its decision to either dose-escalate, proceed to enlargement of the cohort, or explore a lower dose.

If any of the stopping criteria occurred in a subject receiving DNDI-0690 the trial will put on halt and further dosing can be resumed only once an appropriate substantial amendment has been submitted and received regulatory and ethical approval from the relevant ethics committee and competent authority.

Each cohort will follow the same study design including Screening Period, Treatment Period and Post Study Follow-up. The study sequence for Part A is presented in Figure 1.

